**5.2.3.2. ECG Strip Overlay**

1. Strip preparation

- a. The Sponsor will prepare one paired set of rest ECG strips and one paired set of exercise ECG strips from 100 randomly selected subjects (50 AF; 50 SR). Each set of rest and exercise ECG strips will be comprised of the Apple Watch ECG and lead 1 ECG from the 12-lead.
2. Cardiac Core Lab review:
    - a. Three blinded, independent cardiac technicians or cardiologists will review each paired sets of strips on 25mm/s, 10 mm/mV standard.
    - b. One reviewer will identify the first six consecutive distinct readable PQRST complexes without artifact that match between the subject device strip and reference device strip for evaluation. For example, if the reference strip has an artifact in beats 2 and 5 but all other beats are good and the strip from the test device has artifact in beats 1 and 6 but all other beats are good, the six consecutive beats to be used will begin at beat 7 of both strips. The strips will be excluded if six consecutive beats cannot be found. The six PQRST complexes identified by the initial reviewer will be used by the 2 other reviewers.
    - c. The strips will be rendered semi-transparent through the use of back lighting and overlaid to visually assess for morphological similarity.
    - d. Each reviewer will assign a pass/fail to the strips by visually assessing all 6 PQRST complexes. A “pass” is given when the morphology of the PQRST complexes appears to overlay to the unaided eye.
    - e. Measure R amplitude from the isoelectric baseline of the PR segment at the onset of the QRS complex to the highest vertical deflection of the R-wave. Measure to the nearest 0.5 millimeter for the first QRS complex of the six consecutive distinct readable PQRST complexes in both the reference strip and test device strip. The reviewers will be blinded to the identity of the reference strip and test device strip.

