Because data will be collected from the same subjects at rest and after exercise, a bootstrap approach will be implemented to obtain two-sided 95% confidence intervals for the percent correct associated with each of the four secondary endpoint hypotheses to account for potential within-subject correlation. Subjects with at least one adjudicated result of SR (HR 50-99) [hypothesis 2a], AF (HR 50-99) [hypothesis 2b], SR (HR 100-150) [hypothesis 2c], AF (HR 100-150) [hypothesis 2d] and with a classifiable algorithm result will be selected at random with replacement and the 2.5th and 97.5th percentiles of the distribution of bootstrap estimates will represent the two-sided 95% confidence bounds. If the lower confidence bound of the percent correct equals or exceeds the pre-established performance goal associated with the associated secondary endpoint hypotheses, the null hypotheses will be rejected in favor of the alternative hypotheses.

Additional secondary endpoint analyses will be performed similarly by including the HR < 50, HR > 150, and Inconclusive algorithm results in the computations of percent correct.

Two hypotheses associated with secondary objective to demonstrate that the ECG app produces a waveform that provides clinically equivalent information to Lead 1 of the 12-Lead ECG will be tested.

The first hypothesis is aimed at demonstrating that the proportion of subjects with a morphology pass rating based on the visual assessment of 6 consecutive readable PQRST complexes is at least [REDACTED]. The majority result from the pass/fail readings of the 3 independent, certified cardiac technicians will be used for analysis. The hypothesis for this objective is stated as follows:

[REDACTED]  
[REDACTED]

The second hypothesis will be based on the results of the quantitative analysis of the R-wave amplitudes as measured by each of 3 independent, certified cardiac technicians on the paired ECG app and Lead 1 from the 12-Lead ECG reference strips. The majority result from the three

technicians (i.e., if at least two technicians measured the difference in amplitudes between the SUT and reference strips to be  $\leq 2$  mm then the paired strips for a given subject were deemed  $\leq 2$  mm) was used for [REDACTED]

For each subject, the QRS complex from the 12-lead ECG with the largest R amplitude (out of the two QRS complexes with R-wave amplitude measurements) will be used for purposes of determining the majority result.

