### 6.3. Sample Size Determination

[REDACTED] The sample sizes to achieve 80% power with one-sided type I error of 0.025 using exact binomial test are [REDACTED] subjects with no known diagnosis of AF and [REDACTED] subjects with a known diagnosis of AF.

Table 3 below presents the expected percent correct associated with the four secondary endpoints 2a, 2b, 2c, and 2d are summarized below along with the proposed performance goals.

[REDACTED] To account for obtaining readable/classifiable waveforms and to ensure enough data is collected from the exercise stage, 168 subjects with no known diagnosis of AF and 400 subjects with a known diagnosis of AF will be enrolled.

[REDACTED]

[REDACTED] To account for obtaining readable waveforms and to assess waveform equivalence across a range of heart rates and rhythms, approximately 100 subjects (50 SR; 50 AF) will be randomly selected according to the sampling scheme presented in Section 3.4.

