5.2.3.2. ECG Strip Overlay

1. Strip preparation

- a. The Sponsor will prepare one paired set of at rest ECG strips from approximately 100 randomly selected subjects (50 AF; 50 SR) comprised of the Apple Watch ECG and lead 1 ECG from the 12-lead.

2. Cardiac Core Lab review:

- a. Three blinded, independent cardiac technicians will review each paired set of strips on 25mm/s, 10 mm/mV standard.
- b. One reviewer will identify the first six consecutive distinct readable PQRST complexes without artifact that match between the subject device strip and reference device strip for evaluation. For example, if the reference strip has an artifact in beats 2 and 5 but all other beats are good and the strip from the test device has artifact in beats 1 and 6 but all other beats are good, the six consecutive beats to be used will begin at beat 7 of both strips. The strips will be excluded if six consecutive beats cannot be found. The six PQRST complexes identified by the initial reviewer will be used by the 2 other reviewers.
- c. The strips will be rendered semi-transparent through the use of back lighting and overlaid to visually assess for morphological similarity.
- d. Each reviewer will assign a pass/fail to the strips by visually assessing all 6 PQRST complexes. A “pass” is given when the morphology of the PQRST complexes appears to overlay to the unaided eye.
- e. Measure R amplitude from the isoelectric baseline of the PR segment at the onset of the QRS complex to the highest vertical deflection of the R-wave. Measure to the nearest 0.5 millimeter for the first QRS complex of the six consecutive distinct readable PQRST complexes in both the reference strip and test device strip. The reviewers will be blinded to the identity of the reference strip and test device strip.

6. Study Endpoints

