Because data will be collected from the same subjects at rest and after exercise, a bootstrap approach will be implemented to obtain two-sided 95% confidence intervals for the percent correct associated with each of the four secondary endpoint hypotheses to account for potential within-subject correlation. Subjects with at least one adjudicated result of SR (HR 50-99) [hypothesis 2a], AF (HR 50-99) [hypothesis 2b], SR (HR 100-150) [hypothesis 2c], AF (HR 100-150) [hypothesis 2d] and with a classifiable algorithm result will be selected at random with replacement and the 2.5th and 97.5th percentiles of the distribution of bootstrap estimates will represent the two-sided 95% confidence bounds. If the lower confidence bound of the percent correct equals or exceeds the pre-established performance goal associated with the associated secondary endpoint hypotheses, the null hypotheses will be rejected in favor of the alternative hypotheses.

Additional secondary endpoint analyses will be performed similarly by including the HR<50, HR>150, and Inconclusive algorithm results in the computations of percent correct.

Two hypotheses associated with secondary objective to demonstrate that the ECG app produces a waveform that provides clinically equivalent information to Lead 1 of the 12-Lead ECG will be tested.

[REDACTED]

The majority result from the pass/fail readings of the 3 independent, certified cardiac technicians will be used for analysis. The hypothesis for this objective is stated as follows:

[REDACTED]

[REDACTED]

The second hypothesis will be based on the results of the quantitative analysis of the R-wave amplitudes as measured by each of 3 independent, certified cardiac technicians on the paired ECG app and Lead 1 from the 12-Lead ECG reference strips. The majority result

from the three technicians (i.e., if at least two technicians measured the difference in amplitudes between the ECG app and reference strips to be ≤ 2 mm then the paired strips for a given subject were deemed ≤ 2 mm) was used [REDACTED]

[REDACTED]

[REDACTED]

[REDACTED]

For each subject, the QRS complex from the 12-lead ECG with the largest R amplitude (out of the two QRS complexes with R-wave amplitude measurements) will be used for purposes of determining the majority result.

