Due to the multiple observations per subject while at rest and during exercise, a bootstrap approach will be used to construct two-sided 95% confidence intervals for the Morphology Pass Rating Proportion and the R-Wave Amplitude Agreement Proportion. If the lower 2.5th percentile of the bootstrap distribution for the Morphology Pass Rating Proportion [REDACTED], the null hypothesis $H_{0,2e}$ will be rejected. [REDACTED] to the evaluation of the R-Wave Amplitude Agreement Proportion.

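### The analysis unit for endpoint 2f is inconsistent: one QRS complex is kept per subject, although rest and exercise observations are both said to enter the R-wave analysis.

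*SAP*

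**What the plan says.** Four parts of the plan bear on what one observation is for 2f.

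- **Strips prepared.** Protocol 5.2.3.2 item 1a has "one paired set of rest ECG strips and one paired set of exercise ECG strips from 100 randomly selected subjects". SAP 5.2.3.2 item 1a has "one paired set of at rest ECG strips from approximately 100 randomly selected subjects", with no exercise strip.
- **Beats measured.** Item 2e of the same section gives the same rule in both documents: "Measure to the nearest 0.5 millimeter for the first QRS complex of the six consecutive distinct readable PQRST complexes", on the reference strip and on the test strip. That is one QRS complex per strip.
- **Unit of the verdict.** SAP 9.7 takes the majority of three technicians. If at least two find a difference of 2 mm or less, "then the paired strips for a given subject were deemed" to be within 2 mm. A selection sentence then follows in both documents. In SAP 9.7 its core is: "QRS complex from the 12-lead ECG with the largest R amplitude (out of the two QRS complexes with R-wave amplitude measurements) will be used". Protocol 6.2.2 begins it "For each subject, the QRS complex from the 12-lead ECG with the largest R amplitude", and the complex kept is the larger of two measured.
- **Analysis.** SAP 9.7 continues: "Due to the multiple observations per subject while at rest and during exercise, a bootstrap approach will be used" to obtain confidence intervals for both the morphology and the R-wave proportions. Protocol 6.2.2 likewise says that first-trial data at rest and after exercise are used to test both waveform hypotheses.

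The waveform sample, about 100 subjects (50 SR, 50 AF), is sized in part "to assess waveform equivalence across a range of heart rates and rhythms" (Protocol 6.3; SAP 7.1 has the same aim).

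**The concern.** These statements cannot all be followed. A selection that leaves one complex per subject also leaves one verdict per subject. There are then no multiple observations, and no within-subject correlation for the bootstrap to handle. Two analysts working from the same text could compute 2f with a denominator of about 100 or of up to 200.

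More than tidiness is at stake. 2f is formally tested at one-sided 0.025. If the two complexes are the rest and exercise ones, a post-exercise pair that differs by more than 2 mm never counts whenever the rest R wave is the taller, and the reverse also holds. The mix of stages behind the result would be set by reference amplitude and not by design. If only rest strips exist, 2f says nothing about exercise. Either way the intended coverage of a range of heart rates is weakened.

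**Working it through.** The plan's own 2f goal, expected agreement and required sample size are redacted, so there is no stated figure to reproduce. The check is a count, followed by an illustration on assumed values.

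**1. Reference complexes measured per subject** (strip pairs × one QRS per strip)

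- Protocol 5.2.3.2: 2 pairs × 1 = 2, one at rest and one after exercise.
- SAP 5.2.3.2: 1 pair × 1 = 1, at rest only.

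Under the Protocol, the two complexes in the selection sentence can only be one from each stage, since no visible text measures a second beat on a strip. Under the SAP's strip preparation the phrase refers to nothing.

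**2. Observations entering 2f per subject**

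- Selection sentence: 1.
- Analysis paragraphs (Protocol 6.2.2, SAP 9.7): up to 2.

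For 100 subjects this is 100 against up to 200, so up to 100 pairs (half) go unused. The higher figure is a maximum, because strips without six consecutive readable beats are excluded.

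**3. Effect on the estimate (all inputs assumed)**

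Let *p_r* and *p_e* be agreement at rest and after exercise, and *q* the share of subjects whose rest complex is kept, taken as unrelated to agreement.

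- Selection rule: *q·p_r* + (1 − *q*)·*p_e*
- Both stages: (*p_r* + *p_e*)/2
- Shift: (*q* − 0.5)(*p_r* − *p_e*)

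With *p_r* = 0.98 and *p_e* = 0.90, both stages give (0.98 + 0.90)/2 = 0.940.

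| *q* | Selection rule | Shift (points) |
|---|---|---|
| 0.1 | 0.098 + 0.810 = 0.908 | -3.2 |
| 0.3 | 0.294 + 0.630 = 0.924 | -1.6 |
| 0.5 | 0.490 + 0.450 = 0.940 | 0 |
| 0.7 | 0.686 + 0.270 = 0.956 | +1.6 |
| 0.9 | 0.882 + 0.090 = 0.972 | +3.2 |

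If the two stages agree equally often, the shift is zero for every *q*. With *p_e* = 0.80 the range widens to 0.818 to 0.962 around 0.890, or ±7.2 points.

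**4. Effect on precision (assumed agreement 0.95)**

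- One pair per subject: 1.96·√(0.95·0.05/100) = 4.3 points.
- Two pairs per subject with within-subject correlation ρ: 1.96·√(0.95·0.05·(1 + ρ)/200) = 3.0 points at ρ = 0, 3.4 at 0.3, 3.8 at 0.6 and 4.3 at 1.

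**5. Whether the selection can be carried out**

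Three technicians each measure to 0.5 mm, and the text does not say whose reading decides which complex is larger or how ties are broken. In a simulation with an assumed reader SD of 0.35 mm and an assumed SD of 0.5 to 2 mm for the rest-exercise gap, at least one technician had a tie in about 59% down to 22% of subjects. Technicians picked different stages in about 25% down to 8%.

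**The case against.** The strongest reply is that nothing in the plan says the two complexes are one at rest and one after exercise. They might be two beats on one strip, in which case no stage is dropped. Redacted text stands between the majority definition and the selection sentence in the SAP, and may qualify the rule. This stands in part: the stage reading is an inference. But the two-beat reading conflicts with the measurement step, which takes only the first QRS complex, so it moves the inconsistency without removing it.

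One result per subject is also a legitimate unit, and taking the taller R wave may be the stricter test of gain error against a fixed 2 mm limit. Both points are fair. The unit would then need to be stated and justified, and the multiple-observation rationale withdrawn for 2f. A bootstrap on one value per subject is not wrong; it simply lacks the stated reason.

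It could be said that the SAP meant to move to rest strips only. SAP 11 (Changes to Planned Analysis) does not list such a change, SAP 7.2 still blinds technicians to stage, and SAP 9.7 still refers to rest and exercise.

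Three stronger readings are tempting, and the documents do not support them:

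- **That the rule overstates agreement.** The sign depends on which stage tends to have the taller reference R wave and which agrees better. The documents give neither.
- **That it contradicts the aim of covering a range of heart rates.** One complex per subject can still leave a mix of stages and rhythms across subjects. Coverage is weakened and not guaranteed, but it is not negated.
- **That 2e uses both stages while 2f does not.** The analysis paragraphs treat the two endpoints alike, Protocol 6.2.2 also words 2e as a proportion of subjects, and the SAP's rest-only strip preparation applies to both.

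**Conclusion.** The point holds as an inconsistency in the unit of analysis. Strip preparation (rest only in the SAP, both stages in the Protocol), measurement (one QRS complex per strip), selection (one complex of two per subject) and analysis (rest and exercise observations together) cannot all be followed, so 2f is not executable as written. On the only reading that fits the Protocol's strip preparation and measurement, the stage with the smaller reference R wave is dropped and at most 100 of up to 200 pairs are used. On the SAP's strip preparation, exercise is not measured at all.

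The direction and size of any effect on the estimate cannot be determined from the documents. The range of -3.2 to +3.2 points rests on assumed agreement of 98% and 90% and an assumed 10% to 90% of subjects keeping the rest complex. Whether 2f would pass or fail cannot be judged, because its goal is redacted. Confidence is medium, because of the redactions beside the rule. The plan should be corrected, but the matter concerns one secondary endpoint and does not touch the co-primary endpoints.

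**What to change.** 1. Align SAP 5.2.3.2 item 1a with Protocol 5.2.3.2, so that a rest pair and an exercise pair are both prepared for each selected subject.
2. Delete the sentence selecting the largest R amplitude from SAP 9.7 and Protocol 6.2.2.
3. Score each rest and exercise pair as within 2 mm or not, by the three-technician majority.
4. Compute the 2f proportion over all scored pairs. In the bootstrap, resample subjects and carry all of a subject's pairs together; a subject with one usable pair contributes one.
5. Report agreement separately at rest and after exercise, as SAP 9.6 already does for sensitivity and specificity.

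This makes 2f match the analysis that both documents already describe. It works even if two beats on one strip were meant, since no second beat is measured.

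The cost is mainly wording in both documents. The exercise strips must be read, as the Protocol already plans. The estimate may move either way. The sponsor should confirm that the redacted 2f sizing is compatible with a pair-level unit.

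If the sponsor does intend one complex per subject, the plan should justify it, say which stages are measured, whose reading decides the larger complex and how ties are settled, and drop the multiple-observation rationale for 2f.

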9.8. Additional Analyses

The following additional analyses will be performed.

- 1) Percent correct associated with the Other abnormal rhythm truth category will be estimated as $n77/(N7 - n87)$.
- 2) Percent correct associated with the HR under 50 (HR<50 on simultaneous 12-lead ECG) truth category will be estimated as $n11/(N1-n81)$.
- 3) Percent correct associated with the HR over 150 (HR >150 on simultaneous 12-lead ECG) truth category will be estimated as $n66/(N6-n86)$.
- 4) Percent correct associated with the AF rhythm classification for adjudicated heart rate values between 50-120. The numerator of this percent correct calculation will be the number of test device classifications of AF and test device heart rate between 50-120 with an adjudicated AF rhythm classification and adjudicated heart rate value between 50-120. The denominator will include all classifiable test device results with an adjudicated AF rhythm classification and adjudicated heart rate between 50-120.

Two-sided 95% bootstrap confidence intervals will be constructed during the same bootstrap sampling procedure outlined for the primary and secondary endpoints for these four additional analyses. If the number of samples within any of these categories is ≤ 20 , only summary statistics will be presented.

- 5) The number and percentage of the ECG app Inconclusive and the ECG app Poor Recording trials within each category of ground truth will be reported as well as overall as a percentage of the total number of trials.
- 6) A cross-classification table of the ECG app results with each of the types of Other abnormal rhythm truth categories (outlined in Section 5.2.3.1.2) will be presented.
- 7) Descriptive summary statistics (N, mean, std. dev, min, max) of the paired heart rate differences (bpm) between the ECG app and the 12-Lead ECG will be reported by cohort and overall.

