### 6.2.4. Additional Analyses

The following additional analyses will be performed.

- Percent correct associated with the Other abnormal rhythm truth category will be estimated as  $n77/(N7 - n87)$ .
- Percent correct associated with the HR under 50 (HR < 50 on simultaneous 12-lead ECG) truth category will be estimated as  $n11/(N1 - n81)$ .
- Percent correct associated with the HR over 150 (HR > 150 on simultaneous 12-lead ECG) truth category will be estimated as  $n66/(N6 - n86)$ .
- Percent correct associated with the AF rhythm classification for adjudicated heart rate values between 50-120. The numerator of this percent correct calculation will be the number of test device classifications of AF and test device heart rate between 50-120 with an adjudicated AF rhythm classification and adjudicated heart rate value between 50-120. The denominator will include all classifiable test device results with an adjudicated AF rhythm classification and adjudicated heart rate between 50-120.

[figure not shown]
Two-sided 95% bootstrap confidence intervals will be constructed during the same bootstrap sampling procedure outlined for the primary and secondary endpoints for these four additional analyses. If the number of samples within any of these categories is  $\leq 20$ , only summary statistics will be presented.

- The number and percentage of the ECG app Inconclusive and the ECG app Poor Recording trials within each category of ground truth will be reported as well as overall as a percentage of the total number of trials.
- A cross-classification table of the ECG app results with each of the types of Other abnormal rhythm truth categories (outlined in Section 5.2.3.1.2) will be presented.
- Descriptive summary statistics (N, mean, std. dev, min, max) of the paired heart rate differences (bpm) between the ECG app and the 12-Lead ECG will be reported by cohort and overall.

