Because data will be collected from the same subjects at rest and after exercise, a bootstrap approach will be implemented to obtain two-sided 95% confidence intervals for the sensitivity and specificity to account for potential within-subject correlation. Subjects with at least one adjudicated result of AF (for sensitivity), SR (for specificity) and with a classifiable algorithm result (i.e., SR or AF) will be selected at random with replacement and the 2.5th and 97.5th percentiles of the distribution of bootstrap estimates will represent the two-sided 95% confidence bounds. If the lower confidence bounds for both sensitivity and specificity exceed the pre-established performance goal associated with these performance metrics, the null hypothesis will be rejected in favor of the alternative hypothesis. Sensitivity and specificity estimates will also be presented separately for at rest and after exercise measurements along with their corresponding Fisher’s Exact 95% confidence intervals.

As an additional analysis associated with the primary endpoint, the sensitivity and specificity will also be estimated and reported along with their corresponding bootstrap two-sided 95% confidence intervals by including the Inconclusive algorithm classification category in the calculation. More specifically, the sensitivity and specificity for the additional analysis will be estimated as follows:

$$\text{Sensitivity estimate (additional analysis)} = n_{22}/(n_{12} + n_{22}+n_{32})$$

$$\text{Specificity estimate (additional analysis)} = n_{11}/(n_{11} + n_{21}+n_{31})$$

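### SAP 9.8 gives no confidence interval for sparse categories (HR <50, HR >150, possibly Other rhythm) with 20 or fewer samples, although an exact interval is available; minor, descriptive only

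*SAP*

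**What the plan says.** SAP 9.8 lists four percent-correct estimates outside the co-primary and secondary endpoints:

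- Item 1: "Percent correct associated with the Other abnormal rhythm truth category will be estimated as" the ratio n77/(N7 - n87).
- Item 2: "Percent correct associated with the HR under 50 (HR<50 on simultaneous 12-lead ECG) truth category will be estimated as" the ratio n11/(N1 - n81).
- Item 3: "Percent correct associated with the HR over 150 (HR >150 on simultaneous 12-lead ECG) truth category will be estimated as" the ratio n66/(N6 - n86).
- Item 4: "Percent correct associated with the AF rhythm classification for adjudicated heart rate values between 50-120", which has its own numerator and denominator definition.

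On precision the section says: "Two-sided 95% bootstrap confidence intervals will be constructed during the same bootstrap sampling procedure outlined for the primary and secondary endpoints for these four additional" estimates. The exception follows at once. At 20 or fewer samples in any of the categories, "only summary statistics will be presented". Protocol 6.2.4 carries the same exception, beginning "If the number of samples within any of these categories is". Neither document names another interval or says what the summary statistics are for these four items.

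SAP 9.6 uses an exact method for a related purpose: "Sensitivity and specificity estimates will also be presented separately for at rest and after exercise measurements", with exact 95% intervals.

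**The concern.** The rule removes the interval exactly where sampling error is largest. Its motive is sound, because a percentile bootstrap on a handful of binary results is unreliable. That is a reason to change the method, though, and not a reason to report no interval.

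SAP 2.3 says the study supports algorithms that widen the heart-rate range and add new classification results. Items 2 and 3 are the only planned percent-correct figures for recordings whose reference heart rate is below 50 or above 150. If one of these categories is small and every result is right, the report would show 100% with no statement of how far below 100% the true rate could lie.

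**Working it through.** The plan states no figure here to reproduce, and the documents give no category counts. The n and x below are therefore illustrative.

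**1. Exact interval.** Let n be the denominator of the percent correct and x the number correct, with one result per subject. The Clopper-Pearson 95% limits are:

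- lower = Beta quantile at 0.025 with parameters (x, n - x + 1)
- upper = Beta quantile at 0.975 with parameters (x + 1, n - x)

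For x = n the upper limit is 1 and the lower limit reduces to 0.025^(1/n). For example, 0.025^(1/10) = 0.692 and 0.025^(1/20) = 0.832. As a check, the binomial upper tail evaluated at the lower limit is 0.0250 for both 18/20 and 20/20.

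| x/n | Percent correct | Exact 95% interval | Percentile bootstrap |
|---|---|---|---|
| 5/5 | 100% | 47.8-100% | 100-100% |
| 10/10 | 100% | 69.2-100% | 100-100% |
| 9/10 | 90% | 55.5-99.7% | 70-100% |
| 18/20 | 90% | 68.3-98.8% | 75-100% |
| 20/20 | 100% | 83.2-100% | 100-100% |
| 21/21 | 100% | 83.9-100% | 100-100% |
| 30/30 | 100% | 88.4-100% | 100-100% |

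The rows up to n = 20 are those where the plan would show no interval.

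**2. Is the bootstrap rightly withheld?** Coverage is the sum, over all x, of the binomial probability of x times an indicator that the interval contains the true value. At a true percent correct of 90%:

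- n = 10: bootstrap 65.0%, exact 98.7%
- n = 20: bootstrap 87.6%, exact 98.9%
- n = 21: bootstrap 88.7%, exact 98.6%

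Most of the bootstrap shortfall comes from samples with every result correct, where the interval collapses to a point. That probability is 0.9^10 = 34.9% at n = 10 and 0.9^20 = 12.2% at n = 20.

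**3. Does the cutoff of 20 cure this?** No. At n = 21 with all correct, the plan would print 100-100%, against an exact lower limit of 83.9%. Switching to the exact interval for all-correct samples adds back 0.9^21 = 10.9 percentage points. Coverage at n = 21 then rises from 88.7% to about 99.6%.

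**4. Could the rule apply?**

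- *HR <50.* Assume 1% to 3.5% of rest recordings qualify at the planned enrolment of 168 + 400 = 568. Then 568 x 0.01 = 5.7 and 568 x 0.035 = 19.9, so about 6 to 20 recordings. The percentages are assumptions. SAP 11 says enrolment stopped short of target, which lowers these counts.
- *HR >150.* The exercise target in SAP 5.2.1.3 is 0.85 x (220 - age), capped at 150. It falls below 150 from age 44 (0.85 x 176 = 149.6). Subjects are nevertheless meant to exceed their target, so the count could fall on either side of 20.
- *Other rhythm.* The documents offer no basis for a frequency.
- *AF 50-120.* With 400 AF subjects and an assumed 10% contributing a qualifying result, the expected count is 40 and the binomial probability of 20 or fewer is about 0.0002.

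**5. Unit of analysis.** SAP 9.7 lets a subject contribute up to two results, one at rest and one after exercise. If 20 recordings came from 10 subjects whose two results always agreed, 18/20 would carry the information of 9/10. The interval would be 55.5-99.7%, not 68.3-98.8%. The exact intervals in SAP 9.6 avoid this because each stage holds one result per subject.

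**The case against.** The strongest reply is that this is a prespecified reporting choice for descriptive analyses. SAP 7.3 attaches a significance level to the primary and secondary hypotheses only, and items 1-4 are not among them. This stands, and it limits the point to a minor one.

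A reader might infer that the results would appear as bare percentages with the sample size hidden. The documents do not support that. Nothing excludes x/n from the summary statistics, and Table 9.6 shows the counts behind items 1 to 3. Item 5 adds inconclusive and poor-recording counts for each truth category. What is missing is the interval.

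A reader might also infer that all four categories are at risk, or that the rule will certainly apply. Neither follows. AF 50-120 is very unlikely to fall to 20 or fewer, and no count or frequency is given for the other three.

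Finally, the precedent in SAP 9.6 does not carry over directly, because the 9.8 categories pool rest and exercise. An exact interval on pooled recordings would be too narrow if results within a subject agree. That objection is also correct. It bears on how the replacement is worded and does not justify leaving the interval out.

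**Conclusion.** The point holds as a minor reporting weakness. If HR <50, HR >150 or Other rhythm ends with 20 or fewer samples, the plan reports percent correct without an interval, although a valid one is available. For an all-correct result, the omitted lower limit would be 47.8% at n = 5, 69.2% at n = 10 and 83.2% at n = 20.

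These limits assume one result per subject; the counts are illustrative, and whether the rule will be triggered is unknown. The co-primary and secondary conclusions are unaffected. The cutoff also leaves a related gap just above it, where an all-correct category would receive a bootstrap interval of zero width.

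**What to change.** Replace the sentence in SAP 9.8 with:

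> If 20 or fewer samples fall in a category, or if the observed percent correct is 0% or 100% at any n, x/n and percent correct will be presented with an exact (Clopper-Pearson) two-sided 95% confidence interval in place of the bootstrap interval. If any subject contributes both a rest and an exercise result to the category, x/n and the exact interval will be presented separately by stage, as in SAP 9.6, so that each interval uses one result per subject.

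The second sentence fixes the unit in advance and leaves the analyst no choice between recordings. The 0% or 100% clause covers the zero-width bootstrap interval above the cutoff.

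The change needs no new data and little programming. Small categories will visibly show wide intervals, wider still when split by stage. The matching sentence in Protocol 6.2.4 must be amended, which under Protocol 8.1 needs IRB and sponsor approval, or the departure must be recorded in SAP section 11.
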